1.6 CONSORT

The study will be reported in line with the CONSORT (*Con*solidated Standards of Reporting Trials) statement [18].

1.7 Assessment and management of risk

Exercise carries a very small risk of complications. All participants will be assessed for any underlying health conditions or severe complications related to COVID-19. Participants will be excluded from the study at the eligibility stage where exercise is clearly contraindicated, as assessed by a clinical member of the research team. A further assessment will be undertaken by the REGAIN practitioner, through discussion with the patient about their current health, at the time of the initial online intervention assessment. Any additionally identified contra-indications at this stage will result in withdrawal from the study. The REGAIN practitioner will advise on an exercise regime appropriate for each participant's ability. All participants will be advised to have another person nearby for the initial exercise sessions. We will encourage this wherever possible.

All intervention sessions will be led by staff experienced in assessment, prescription and delivery of exercise for multi-morbid clinical populations.

For the exercise programme, weekly troubleshooting will assess safety, progress, changes to health, and any adverse effects. This will take place during a 10 minute 'debrief' after each live online exercise session every week. Participants will have the opportunity to attend the troubleshooting session at least weekly to discuss any issues with the REGAIN practitioners and other participants. There will also be time to discuss these issues after each of the group behavioural sessions, and participants may contact the REGAIN practitioners or the study team via email or telephone with any further queries.

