Study staff will ensure that participants' anonymity is maintained. Participant identifiable information will be stored securely on the electronic database. All data will be stored securely and will only be accessed by study staff and authorised personnel. The study will comply with relevant UK data protection legislation, which requires data to be pseudonymised as soon as it is practical to do so. Identifiable data will be deleted within 6 weeks of completion of the study, specified as the point of withdrawal or completion of the 12 month follow-up questionnaire.

One ethical consideration is that people of different ethnicities can take part in the study. Participants who are not fluent in spoken or written English will be eligible to take part. Participant information sheets and consent forms will be translated into the following languages; Bengali, Gujarati, Urdu, Punjabi and Mandarin. When confirming consent for those not fluent in English, a bilingual researcher will speak to the participant to ensure a full explanation of the study and to confirm understanding. An NHS accredited translator will be included in the one-to-one advice consultation (control arm) and the individual assessment (intervention arm). On-demand online videos will also be translated in those languages mentioned above. Participants who are not fluent in English will be encouraged to attend live online exercise sessions with a friend or relative who can translate for them. For the psychological support sessions we will arrange bespoke small online group sessions with an REGAIN practitioner and NHS accredited translator. A core data outcome set including the PROMIS[®] 29+2 Profile v2.1 (PROPr) and EQ-5D-5L questionnaires will be collected orally by a bilingual researcher, where necessary, to ensure that those not fluent in English are able to contribute participant reported outcomes to the study.

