2.4.2 Exclusion criteria

- 1. Exercise contraindicated*
- 2. Severe mental health problems preventing engagement**
- 3. Previous randomisation in the present study
- 4. Patient already engaging in, or planning to engage in a conflicting NHS delivered rehabilitation programme in the next 12 weeks
- 5. A member of the same household has previously been randomised in the present study

* As advised by a clinical member of the research team or REGAIN practitioner

** Self-reported and/or adjudged by a clinical member of the research team or the REGAIN practitioner

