2.6 Eligibility and informed consent

When a potential participant has registered their eligibility and expression of interest for the REGAIN study via the online database, the WCTU REGAIN study team and the site team based at UHCW will receive an alert. An appropriately trained clinical member of the site team (listed on the study delegation log) will then telephone the potential participant on their main telephone contact number. The REGAIN site team member will conduct a further eligibility screen and complete an online eligibility form with the potential participant. The REGAIN site team member will ensure the potential participant has read the PIS, understands what is involved and has had the chance to ask any questions before starting the eligibility questions.

If the potential participant is eligible for the REGAIN study, they will automatically receive a link via text or email (whichever they have specified is their preference) to an electronic consent form. The team member will explain the purpose of the consent form and summarise the key points. The patient will be able to complete the consent form in their own time, although the link will only be active for three weeks from the date sent. Upon clicking the link to the consent form, the participant will be issued with an authentication code via text or email, ensuring only the intended patient can access the consent form via the sent link. Potential participants will need to confirm they have read each of

the consent items before agreeing to take part in the study. A copy of the fully signed consent will then be sent to the patient via email. Once the consent form has been completed, the participant will be able to access the baseline questionnaire from the same link. Once both the consent form and baseline questionnaires have been completed by the patient, they will be automatically randomised into the study by the online system.

Pregnancy is not an exclusion criterion for REGAIN. These potential participants will be recruited to the study if eligible and participants who confirm pregnancy following enrolment will remain in the study. All participants randomised to the intervention arm, including those who are pregnant, will receive a one-to-one consultation with a REGAIN practitioner where exercise will be tailored to their ability, however, the exercise intervention is deemed safe for those who are pregnant. These participants will be monitored for adverse events as per Section 4.

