2.8.2 Post-randomisation withdrawals and exclusions

Participants may decline to continue involvement in the study at any time, without prejudice. This will not affect the standard of care they receive. For participants withdrawing from the study, data obtained prior to the point of withdrawal, will be retained for the final analysis unless explicitly withdrawn at the participant's request. For participants who withdraw, a withdrawal CRF will be completed.

Participants may be withdrawn from the study, at any time, at the discretion of the investigator /practitioner based at UHCW or the Trial Steering Committee due to safety concerns.

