Data will still be collected for participants who discontinue or deviate from the intervention protocol, unless they withdraw their consent (section 2.9.2). For any participants who do not respond to the 12 month follow-up questionnaire, WCTU will request a copy of the participant's medical record from their GP. Identifiable data will be deleted within 6 weeks of completion of the study, specified as the point of withdrawal or completion of the 12 month follow-up questionnaire.

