#### 3 ANALYSIS

#### 3.1 Subject population

#### 3.1.1 Intention-to-treat

The primary analysis and any secondary analyses will be applied to an all-randomised population on an intention-to-treat (ITT) basis. That is, any subject randomised into the trial, regardless of whether they received trial intervention and regardless of protocol deviations, unless specified.

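### A contraindication found after randomisation, at an assessment only the intervention arm has, leads to study withdrawal; this conflicts with the protocol's follow-up rule and risks losing the three-month outcome in one arm

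*Protocol*

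**What the plan says.** - **Order of events.** Once consent and the baseline questionnaires are complete, Protocol 2.6 says of participants that "they will be automatically randomised into the study by the online system".
- **The later check.** Protocol 1.7 adds a second look at the initial online intervention assessment: "A further assessment will be undertaken by the REGAIN practitioner, through discussion with the patient about their current health". Protocol 2.9.1 makes that assessment the first component of the REGAIN intervention. Protocol 1.5 assigns the assessment to the intervention arm and an advice consultation to the control arm.
- **The consequence.** Protocol 1.7: "Any additionally identified contra-indications at this stage will result in withdrawal from the study".
- **The control session.** Protocol 2.9.1 describes a 30-minute advice consultation and states no contraindication check or mandatory withdrawal for it.
- **What study withdrawal means.** Protocol 2.6 treats leaving the study and leaving the intervention as separate options. Protocol 2.8.2 says that data from before withdrawal are retained. Protocol 1.5 and 5.1 have identifiers deleted within six weeks of withdrawal.
- **The follow-up rule.** Protocol 5.1: "Data will still be collected for participants who discontinue or deviate from the intervention protocol, unless they withdraw their consent".
- **The analysis population.** SAP 3.1.1 covers "any subject randomised into the trial, regardless of whether they received trial intervention and regardless of protocol deviations".

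**The concern.** Section 1.7 names the study, not the intervention, as what the participant leaves, and the protocol distinguishes the two elsewhere. A practitioner's finding is not a withdrawal of consent. A participant stopped for this reason is therefore removed under 1.7 but followed up under 5.1, and staff cannot do both.

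If 1.7 is followed, people whose health has been judged unsuitable for exercise lose their primary outcome after allocation, and only in the arm that has the assessment. Their counterparts in the control arm remain and are measured. If those removed would have scored lower on PROPr, the observed intervention mean is too high and the comparison favours REGAIN. They would also miss the three-month questionnaire, which Protocol 4.2.3 uses in both arms to detect possible serious adverse events.

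**Working it through.** **1. Would the primary outcome be lost?** Suppose the assessment takes place in week 1 or 2 (an assumption; the documents give no date). Deletion of identifiers is then due by week 1 + 6 = 7 or week 2 + 6 = 8. Three months is about 13 weeks, and the window in Protocol Table 1 is ±2 weeks, so it opens at about 13 − 2 = week 11. Contact details would be gone before the questionnaire is due. With only earlier data said to be retained, the normal result is no three-month PROPr.

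**2. Would the analysis correct for it?**
- The primary model (SAP 5.1.1) adjusts for baseline, age, level of hospital care and case-level mental health disorder. It does not impute.
- Imputation is a sensitivity analysis, run only if judged appropriate (SAP 3.1.2 and 5.4.2).
- Adjustment helps to the extent that those baseline variables explain both the contraindication and the outcome. A problem first found after baseline may not be fully captured by them.

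**3. The plan's own figure.** Inputs from Protocol 6.1: effect 0.3 SD, 90% power, 5% type I error (two-sided, SAP 5.5), ICC 0.01, groups of 8, 10% loss.
- Design effect in the intervention arm: 1 + (8 − 1) × 0.01 = 1.07. Allocation ratio: √1.07 = 1.034.
- Control: (1.960 + 1.282)² / 0.3² × (1 + 1.07/1.034) = 237.5. Intervention: 1.034 × 237.5 = 245.7.
- Total: 483.2 / 0.9 = 536.9, against the stated 535. The figure is reproduced.
- Standard error at the planned size after 10% loss: √(1.07/244.8 + 1/236.7) = 0.093 SD.

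Power is not the issue. A further 10% loss in the intervention arm alone leaves it at 88.3%.

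**4. Size of the bias.** Let p be the share of the intervention arm removed and d the amount, in SD, by which their mean PROPr lies below that of those who remain. The full-arm mean is then lower than the observed mean by p × d, and that is the bias. Both inputs are assumptions.

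| p | People out of 272 | d | Bias | Share of 0.3 SD |
|---|---|---|---|---|
| 2% | 5.4 | 0.5 | 0.02 × 0.5 = 0.010 SD | 3% |
| 5% | 13.6 | 1.0 | 0.05 × 1.0 = 0.050 SD | 17% |

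Against the standard error of 0.093, these are about 0.1 and 0.5 standard errors.

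**5. Wider range.** If the gap D is measured from the full-arm mean instead, the bias is p × D / (1 − p). Over p from 1% to 10% and D from 0.5 to 1 SD it runs from 0.005 to 0.111 SD, and two-sided type I error runs from 5.0% to 21.5%. If baseline adjustment removed half, the worst case would fall to 0.056 SD and 9.0%.

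**The case against.** **The wording of 1.7 may be loose.** It does not itself say that follow-up ends, and 5.1 could be read as governing. That is possible, but the retention sentence in 2.8.2 and the deletion rule point the other way. The documents leave the matter open, which is reason enough to reconcile them.

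**The numbers may be tiny.** Anyone affected has already passed online screening and a clinical telephone check, and the primary model adjusts for baseline. This stands: at 1–2% removed, the bias is at most about 0.02 SD.

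**Much of the reporting is already planned.** SAP 3.1.2, 4.1 and 4.3 cover reasons for withdrawal, participant flow and losses by arm. This stands too; what is missing is a separate count for this reason.

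A reader might also infer more than the documents support:

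- **That the rule contradicts intention-to-treat.** It does not. SAP 3.1.1 still counts these people in their allocated arm. The problem is missing outcomes.
- **That it operates throughout treatment.** Section 1.7 ties it to the initial assessment, not to the later weekly contact.
- **That all safety withdrawal falls on one arm.** Protocol 2.8.2 allows withdrawal for safety concerns "at the discretion of the investigator /practitioner based at UHCW" or by the Trial Steering Committee, in either arm. The exclusion footnote in 2.4.2, "As advised by a clinical member of the research team or REGAIN practitioner", is not limited to one arm either, and controls also meet a practitioner. Only the mandatory rule in 1.7 is specific to one arm.

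**Conclusion.** The conflict between Protocol 1.7, read with 2.8.2, and the follow-up rule in 5.1 is real. Following 1.7 as written would normally lose the three-month PROPr for participants selected on health, after randomisation, through a rule that applies in one arm.

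The direction of bias is not established. No passage links a late contraindication to lower PROPr. It is a reasonable assumption, and under it the bias favours REGAIN. The size is unknown because no rate is given: about 0.01 SD (2% removed, 0.5 SD worse) to 0.05 SD (5%, 1 SD), before a baseline adjustment that may remove part of it. The bias becomes material only if late contraindications are more common than 1–2%. The point should be corrected, but these figures do not make it a condition of accepting the plan.

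**What to change.** Leave the clinical decision about exercise, and the safety discretion in Protocol 2.8.2, exactly as they are. Change only what follows for data.

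1. Reconcile 1.7 and 2.8.2 with 5.1. State that a participant found to have a contraindication after randomisation stays in the 3-, 6- and 12-month questionnaire follow-up unless they themselves withdraw consent, and is analysed as randomised. It follows that the finding alone does not start the six-week deletion of identifiers.
2. For anyone already withdrawn under this rule, seek the remaining follow-up data only where consent and retained contact details allow. The deletion rule may make this impossible for some.
3. Report the number withdrawn for this reason, by arm, in the CONSORT chart planned in SAP 4.1. That count replaces the assumed p above.

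**Cost.** A minor protocol amendment and a note to the delivery team. No visits are added, because online questionnaires and telephone collection of the core outcomes already exist. The effect estimate may be slightly smaller. SAP 2.8 reports recruitment complete at 585, so the new wording will reach few, if any, new first assessments; its main value is for remaining follow-up and reporting.

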Pre-pilot: A small pre-pilot feasibility phase (n= 6-10) will be undertaken to complete development of intervention and study materials, refine online recruitment processes, pilot practitioner training, and confirm feasibility of intervention delivery using live and recorded online sessions. Over one month, the constituent parts of the REGAIN intervention will be tested with six to ten participants recruited from our PPI group. These participants will not be allocated a REGAIN study number and no data from these participants will be analysed as part of the study outcomes. The purpose of this pre-pilot will be to refine and test the online delivery of intervention and control materials, including participant and practitioner manuals, and staff training procedures, and to commence preparation for main study set-up. This will allow us to confirm the feasibility of all aspects of the study and make final alterations prior to the internal pilot.

Internal pilot: In a one-month internal pilot (n=35), recruiting from multiple PIC sites and running seamlessly into the main study, participant recruitment and retention will be confirmed. This will also provide provisional data on the fidelity of the intervention, its safety, and participant compliance and experiences.

Figure 1 Study flow diagram

2.2 Aims and objectives

The aim of this study is to assess the clinical and cost effectiveness of an intensive, on-line, supervised, group, home-based rehabilitation programme (the REGAIN intervention) compared to best practice usual care (single advice session only), to support long-term physical and mental health recovery for people discharged from hospital more than three months after COVID-19 infection.

2.2.1 Primary objective

The primary objective of this study is to determine if the REGAIN rehabilitation intervention improves HRQoL at three months post-randomisation compared to best-practice usual care in patients with ongoing COVID-19 symptoms.

2.2.2 Secondary objective

Secondary objectives of the study are to determine if the REGAIN intervention compared to bestpractice usual care in patients with ongoing COVID-19 symptoms impacts on the following outcomes over 12 months:

- 1. HRQoL
- 2. Dyspnoea
- 3. Cognitive function
- 4. Health utility
- 5. Physical activity
- 6. PTSD symptom severity
- 7. Depressive and anxiety symptoms
- 8. Work status
- 9. Health and social care resource use
- 10. General health
- 11. All-cause mortality.

2.2.3 Symptoms sub-study objective

To report on the characteristics of people discharged from hospital with COVID-19, we will ask participating NHS Trusts to provide pseudonymous key demographic data to allow comparison of recruited and non-recruited patient cohorts. We will record and compare selected factors including patient factors (ethnicity, age, gender) and COVID-19 admission characteristics (duration of hospital stay, need for high flow oxygen/continuous positive airways pressure/ventilation), and ongoing COVID-19 symptom profile.

2.2.4 Process Evaluation objective

- 1) To explore the experiences of participants in the intervention and control groups, including enablers of, and barriers to, lifestyle change amongst participants.
- 2) To highlight any contextual issues that may affect the outcome or delivery of the study and/or intervention.

2.3 Outcome measures

2.3.1 Efficacy

Primary Outcome:

Health-related quality of life (HRQoL) measured using the PROMIS[®] 29+2 Profile v2.1 (PROPr) at three months post-randomisation. This measure is part of a portfolio of outcomes developed and validated by the National Institute for Health (NIH) (USA); the Patient-Reported Outcomes Measurement Information System. It is a reliable generic outcome measure validated for on-line use [19-21] generating a single overall score plus physical function, anxiety, depression, fatigue, sleep disturbance, social roles/activities, pain interference, cognitive function and pain intensity sub-scales.

Justification for timing of primary outcome

Long-term outcomes are important, however, any intervention effects will be maximal soon after completion of the intervention. We have set our short-term follow-up at three months as we are confident that those randomised to the REGAIN intervention will complete the eight-week treatment phase in this time period. If there is no evidence of effect at three months, then a meaningful effect at one year is unlikely. Assessing the primary outcome at three months after randomisation is more efficient than seeking an effect at one year, as attrition will be lower.

Secondary Outcomes:

The following outcomes will be measured at three, six and 12 months post-randomisation.

- 1. HRQoL: PROPr
- 2. Dyspnoea: PROMIS dyspnoea severity Short Form [21]. Exertional dyspnoea is a commonly reported symptom in COVID-19 survivors, so we have added specific questions to the longer HRQoL PROMIS measure.
- 3. Cognitive function: PROMIS Neuro-QoL Short Form v2.0 Cognitive Function [21]. In light of the apparent high incidence of cognitive impairment in COVID-19 survivors we have added additional PROMIS questions, to obtain a specific measure of cognitive function.
- 4. Health utility: Euroqol EQ-5D-5L [22]. Validated, generic HRQoL measure consisting of five dimensions, each with five levels. Each combination of answers can be converted into a health utility score. It has good test-retest reliability, is simple to use, and gives a single preference-based index value for health status that can be used for cost-effectiveness analysis.
- 5. International Physical Activity Questionnaire (IPAQ short-form). A well-established activity measure reported as metabolic equivalent task (MET)-minutes per week derived from duration of walking, moderate and vigorous exercise [23]
- 6. PTSD symptom severity: The Impacts of Events Scale-Revised (IES-R) a 22 item self-report measure of difficulties people sometimes face after stressful life events. It has been widely used in studies of survivors of ICU admission, including COVID admissions. It is part of recommended outcomes for studies of respiratory failure survivors [24-26]. A score of ≥11 on the IES-6, an abbreviated version extracted from the longer 22-item IES-R, will be taken to be indicative of case level disorder.
- Depressive and anxiety symptoms: Hospital Anxiety and Depression Scale (HADS). A 14-item questionnaire from which anxiety and depression subscales can be derived. 7 item sub-score values ≥11 points identify case-level anxiety/depression. Commonly used and well validated measure in clinical populations [27].
- 8. Work status: Time lost from work (paid/unpaid) and patient-borne health costs.

- 9. Health and social care resource use: participant self-report and NHS records. The primary health-economic analysis will concentrate on direct intervention and healthcare/personal social services costs, while wider impact (societal) costs will be included within the sensitivity analyses. Participants will complete resource use questionnaires at all follow-up points, to collect resource use data associated with the interventions under examination. We will request a copy of the participant's medical record from their GP at the end of the study follow-up if the participant has not responded to the 12-month follow-up or if we know the participant has died. This will provide information on GP consultations and include copies of any hospital discharge letters allowing us to accurately cost in-patient care costs. Where appropriate we will triangulate data from GP records and participant self-report to achieve a robust estimate of health service activity. Consent will be obtained for access GP records.
- 10. General health Participant self-reported measurements of current overall health and comparison of current health to health 12 months prior.
- 11. Death measured using GP.

Follow-up: Patient reported outcomes will be collected online at baseline pre-randomisation, three months, six months and 12 months post-randomisation. Participants will receive an email notification and/or text message to remind them to complete the online questionnaires at each follow-up time point. In the case of non-response, two key outcomes, the PROPr (primary outcome) and EQ-5D-5L will be collected by telephone. Fluency in English is not an inclusion criterion for this study. For those not fluent in English, we will aim to collect all outcomes (or as many as possible) verbally at each follow-up. As a minimum, a core data outcome set including the PROMIS® 29+2 Profile v2.1 (PROPr) and EQ-5D-5L questionnaires will be collected orally by a bilingual researcher, where necessary, to ensure that those not fluent in English are able to contribute participant reported outcomes to the study. The EQ-5D-5L is well validated for verbal administration.

Long-term follow-up: Consent will be sought from participants to hold their personal data, and at the end of the 12-month follow-up period, to request a copy of the participant's medical record from their GP. This will only be requested if the participant has not responded to the 12-month follow-up or if we know the participant has died. This will provide information on GP consultations and include copies of any hospital discharge letters allowing us to accurately cost in-patient care costs. Where appropriate, we will triangulate data from GP records and any participant self-report to achieve a robust estimate of health service activity and mortality.

